Attempts have been made with various agents to reduce the development of tolerance and hyperalgesia following remifentanil. Postoperative hyperalgesia and its prevention has been studied with ketamine[10, 11, 15-36], Magnesium [12, 34, 37], Gabapentin[16], Clonidine[19, 38], Lornoxicam [18], Dextromethorphan [39], Paracetamol [40, 41], Morphine [42], Dexmedetomidine [43], Adenosine [44, 45], COX inhibitors [46, 47], Amantadine [48], Nitrous oxide [49], Fentanyl [50], Pregabalin [51], Buprenorphine [52], Midazolam [53], Dexamethasone [36]. Relevant to our current hypothesis is the report that concomitant administration of ultra-low dose naloxone [13] and naltrexone [54] with remifentanil prevented OIH. However, there are no studies on reducing the adverse effects of remifentanil with ultra-low dose naloxone in human subjects. While the traditional role of opiate antagonists have been in cases of opioid overmedication, recent evidence is emerging regarding their use in pain management. Gan et al. 1997 used an ultra-low dose naloxone infusion (0.00025 mg/kg/h or 0.001 mg/kg/h) in postoperative patients receiving IV morphine via a patient-controlled analgesia (PCA) device. Good pain relief was experienced in all groups, however consumption of PCA morphine was significantly reduced in patients that received the lowest infusion of naloxone and opioid-induced side effects (nausea, vomiting, pruritus) were reduced by naloxone at both dose.

Describe the primary outcome variable(s), secondary outcome variables, and predictors and/or comparison groups as appropriate for the stated study objectives/specific aims:

The primary outcome variable of the study will be to determine the occurrence of OIH in high dose remifentanyl treatment group compared to a low dose Remifentanyl group and a high dose Remifentanyl dose with ultralow dose naloxone. OIH will be determined by assessing evoked pain thresholds. Secondary outcomes will include verbal assessment of overall pain levels via validated standard pain questionnaires and post-operative opioid consumption to determine presence of opioid analgesic tolerance. The predicted outcome is that ultralow dose naloxone will attenuate the development of remifentanyl-induced OIH. Primary outcome: Mechanical pain threshold, determined by von Frey filaments, around the incision site at 24 and 48h post-surgery. Primary hypothesis: The mechanical pain thresholds at 48h in the HN group is higher than in the HI group. Secondary

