 Subjects screened for inclusion/exclusion criteria Study introduction  
 during surgical consult visit Subjects provided with consent form and study  
 information sheet 2 Lab Visit Initiate subject consent Hamilton Rating  
 Scale, VAS, McGill Pain Questionnaire, Brief Pain Inventory Finalize Consent  
 3 Pre-Surgery Subject is greeted in preop area Von Frey Testing, Cold  
 Pressor Test, Opioid Consumption Pre-surgery medication: standard-of-  
 care 4 Surgery Group 1 (LO): Induction dose per anesthesiologist (no  
 ketamine); Maintenance: 0.1mcg Remifentanyl Group 2 (HI): Induction dose  
 per anesthesiologist (no ketamine); Maintenance: 0.4mg Remifentanyl +  
 Saline Group 3 (HN): Induction dose per anesthesiologist (no ketamine);  
 Maintenance: 0.4mg Remifentanyl + 0.004mcg/kg/min Naloxone 5 Post-  
 Surgery Post-surgery medication: standard-of-care @4H, @8H, @ 12H: VAS,  
 Opioid Consumption @24H: VAS, Von Frey Testing, Cold Pressor Test,  
 Opioid Consumption @48H: Hamilton, VAS, McGill, Brief Pain Inventory,  
 Von Frey, Cold Pressor, Opioid Consumption UCI IRB

Provide precise definitions of the study endpoints and criteria for evaluation; if the primary outcomes are derived from several measurements (i.e., composite variables) or if endpoints are based composite variables, then describe precisely how the composite variables are derived:

see above

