### **Statistical Considerations**

Is a statistical analysis plan appropriate for this qualitative study design?

Yes

Describe the statistical methods for the stated specific aims and hypotheses. Your analysis plans should match the stated study specific aims and hypotheses:

For the primary outcome, the 2-sample t-test will be applied to compare the difference in mechanical pain thresholds at 24 and 48h between HN and HI group, and between LO and HI group. For the secondary outcomes, the continuous variables will also be analyzed using 2-sample t-test to identify the difference between HN and HI group, and between LO and HI group. The mean level and corresponding 95% confidence interval (CI) will be

obtained for each study group. The categorical outcomes will be analyzed using the chi-square test and the odds ratio (compare to HI group) and corresponding 95% CI will also be obtained.

Describe the statistical method(s) that will be used to analyze the primary outcome(s) or endpoints:

see above

If appropriate describe secondary or post hoc analyses of primary outcome(s) or other exploratory analysis and if necessary, provide a breakdown of the methods used per outcome or endpoint:

Secondary outcomes: - Opioid consumption required to control pain over the first 24 and 48h post-operatively. - Cold pressure test for pain threshold and pain tolerance - VAS pain scores measured prior to surgery and at 4, 8 and 12h after extubation and again at 24h and 48h post-operatively. - McGill short form questionnaire to be filled out prior to surgery and at 48h post-operatively - Brief Pain Inventory questionnaire to be filled out prior to surgery and at 48h post-operatively

**Sample Size Determination:** Explain how the overall target sample size was determined (e.g., power analysis; precision estimation), providing justification of the effect size for the primary outcome based on preliminary data, current knowledge/literature and/or cost consideration; if appropriate, provide sample size justification for secondary outcomes. Power analysis should (at least) match the primary outcome/endpoint:

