The sample size determination and power analysis was based on a 2-sided 2-sample t-test with a significant level of 0.05. The following table shows the minimum effect size to detect for various sample size and power. We propose to recruit a total of 105 subjects (35 per group) and expect to have 96 subjects (account for 8% attrition) for final analysis. The proposed sample size will provide the study 80% power to detect an effect size of 0.71 and 90% power to detect an effect size of 0.82.

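### Opioid consumption is compared by an unadjusted t-test on arm means, which ignores the preoperative opioid use already scheduled and has no check against a few heavy users

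*Combined protocol and SAP*

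**What the plan says.** Under Background & Purpose of the Research, the plan gives the outcome its role: "post-operative opioid consumption to determine presence of opioid analgesic tolerance". Statistical Considerations lists it as "Opioid consumption required to control pain over the first 24 and 48h post-operatively".

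The same section fixes the method for all continuous secondary outcomes: "For the secondary outcomes, the continuous variables will also be analyzed using 2-sample t-test to identify the difference between HN and HI group", and likewise for LO against HI. On summaries it says "The mean level and corresponding 95% confidence interval (CI) will be" obtained for each group. It names no covariate, transformation, rank test, outlier rule or common opioid unit.

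Three other places bear on this:

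- The visit schedule under Study Design lists opioid consumption at the pre-surgery step, as well as at 4, 8, 12, 24 and 48 hours.
- The schedule describes postoperative treatment only as "Post-surgery medication: standard-of-care".
- The exclusion criteria remove a history of substance abuse and chronic pain other than the surgical indication. They do not list preoperative opioid use.

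**The concern.** Patients having posterior spinal fusion may enter with painful spinal disease and already on opioids. Preoperative consumption is then a plausible predictor of postoperative consumption. A t-test that leaves it out treats predictable between-patient variation as noise, although the plan already schedules the measurement.

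Dose totals also cannot fall below zero and may have a long upper tail. If they do, two or three heavy users in a group of 32 can move the arm mean and inflate its standard error, and the plan has no second analysis that would show it. The stake is the tolerance part of the study purpose: a real difference could be missed, or an apparent one could rest on a few patients.

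**Working it through.** **Inputs.** From Statistical Considerations: a calculation "based on a 2-sided 2-sample t-test with a significant level of 0.05"; 105 recruited (35 per group); 8% attrition; 96 analysed (32 per group); effect sizes 0.71 (80% power) and 0.82 (90%). The documents give no mean, SD, distribution or baseline correlation for opioid dose. All of these are assumed below and shown as ranges.

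**1. The plan's own figures.** Noncentral-t power with 32 per group is 79.8% at 0.71 and 89.8% at 0.82. Recruitment: 96 / (1 − 0.08) = 104.3, rounded up to 105. Both reproduce. The effect sizes are generic, and the plan claims no power for opioid consumption.

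**2. Precision given up by ignoring baseline.** With correlation r between preoperative and postoperative consumption, ANCOVA multiplies the residual SD by √(1 − r²). The effect in residual-SD units becomes 0.71 / √(1 − r²). With 32 per group and 61 degrees of freedom (64 − 3):

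| r (assumed) | √(1 − r²) | Effect | Power |
|---|---|---|---|
| 0 | 1.000 | 0.710 | 79.8% |
| 0.3 | 0.954 | 0.744 | 83.4% |
| 0.5 | 0.866 | 0.820 | 89.8% |

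Simulating the fitted ANCOVA (normal data, 20,000 trials), which also counts the cost of estimating the slope, gives 79.7%, 83.2% and 89.4%. At r = 0.5 the gain is like having 32 / 0.75 = 42.7 patients per group. At r = 0 almost nothing is lost.

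**3. Right tail, log-normal doses.** With s the SD of log dose, CV = √(exp(s²) − 1). The arm ratio is set to exp(0.7115 s), so that the log-scale t-test has 80% power. Simulated power at 32 per group (repeat runs differ by 1 to 2 points):

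| CV | t-test on dose | t-test on log dose | Loss, points |
|---|---|---|---|
| 0.66 | 74% | 80% | 6 |
| 0.95 | 68% | 80% | 12 |
| 1.3 | 62% | 80% | 18 |
| 1.8 | 54% | 80% | 26 |

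The rank-sum test has 77 to 78% throughout.

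**4. The same CVs and arm ratios with gamma doses**, which are also positive and right-skewed:

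| CV | t-test on dose | t-test on log dose |
|---|---|---|
| 0.66 | 71% | 63% |
| 0.95 | 64% | 49% |
| 1.3 | 52% | 32% |
| 1.8 | 37% | 18% |

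The ranking reverses. The rank-sum test lies between the two: 65%, 54%, 39% and 25%.

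**5. A heavy-user minority.** Take gamma doses with CV 0.5 and an arm ratio of 1.5. Power for t-test / log t-test / rank-sum is 88/84/85% with no heavy users. It is 70/79/80% if 5% of patients need three times the usual dose, and 58/72/75% if 10% do. So the gamma advantage can vanish with a small subgroup.

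**6. Influence.** In a log-normal group of 32, the three largest values hold on average 63% of the sum of squares at CV 1.0 and 70% at CV 1.5, against 30% for normal data.

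**7. False positives.** Simulated type I error of the t-test is 3.9 to 5.0% (log-normal) and 4.6 to 5.1% (gamma), so it is not inflated.

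**8. The trial as closed.** Eight participants were enrolled. If all three groups have at least one, any two groups hold at most 7. The smallest two-sided exact rank-sum p-value is then 2 / C(7,3) = 2/35 = 0.057. With an assumed 3/3/2 split it is 2/20 = 0.10 (3 against 3) or 2/10 = 0.20 (3 against 2).

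**The case against.** The strongest reply is that the planned test is valid and its target reasonable. A difference in mean total dose is a legitimate measure of consumption, the type I error holds, and no stated power figure is wrong. Each formal hypothesis concerns mechanical pain thresholds; opioid consumption is one item in a list of secondary outcomes. All of this stands.

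A reader might infer that the t-test simply loses power on skewed dose data and should give way to a log-scale analysis. The documents do not support that. They say nothing about the shape of the doses, and steps 3 and 4 show that the sign of the power difference depends on which skewed distribution is assumed. Log-normal data favour the log analysis by construction. The documents also never say that untransformed totals will be used; this is inferred from their silence and from the reporting of means.

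Nor would a rule to switch to a rank test if any total is zero be an improvement. One patient's value would then change both the test and the quantity estimated, and the rank-sum test cannot carry the baseline covariate.

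The reply does not explain why a scheduled baseline goes unused, or why no sensitivity analysis is planned.

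**Conclusion.** The point holds in two parts, both modest.

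- **Unused baseline.** Adjustment would raise power from about 80% to 83–89% at an effect of 0.71 and 32 per group, for an assumed correlation of 0.3 to 0.5. With no correlation there is no gain and practically no cost.
- **Exposure to heavy users.** This rests on an assumed heavy right tail, which the eligibility rules permit but the documents do not show. The power difference against a log-scale test runs from a loss of 6 to 26 points (log-normal, CV 0.66 to 1.8) to an advantage for the planned test (gamma).

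This is a matter of efficiency and robustness in a secondary outcome. It does not affect the primary comparison or the sample-size calculation. The power figures describe the trial as planned; with 8 participants no choice of test would make this comparison informative.

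**What to change.** For the trial as planned, replace the t-test for this outcome with wording to this effect:

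- Opioid consumption over 0–24 h and 0–48 h is converted to one common opioid-equivalent unit and totalled per patient.
- The main estimate is the difference in mean total dose with 95% CI, for HN against HI and LO against HI, from a linear model with treatment group and preoperative opioid consumption as covariate. The unit and look-back window for the preoperative value are defined in advance.
- One sensitivity analysis is run whatever the data look like: the Wilcoxon rank-sum test with the Hodges–Lehmann shift and its 95% CI. It is unadjusted, and nothing in the data triggers a switch of method.

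For the 8 participants enrolled, report individual values and medians by group, with preoperative consumption alongside, and no test. The closure form says the analysis has not been done, so this can be written down first.

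The cost is a few sentences in the analysis plan, one conversion table and one degree of freedom. No new assessment is needed, because preoperative consumption is already on the schedule.

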hypotheses: 1. The mechanical pain thresholds at 48h in the LO group is higher than in the HI group. 2. The mechanical pain thresholds at 24h in both HN and LO group is higher than in the HI group. Secondary outcomes: - Opioid consumption required to control pain over the first 24 and 48h post-operatively. - Cold pressure test for pain threshold and pain tolerance - VAS pain scores measured prior to surgery and at 4, 8 and 12h after extubation and again at 24h and 48h post-operatively. - McGill short form questionnaire to be filled out prior to surgery and at 48h post-operatively - Brief Pain Inventory questionnaire to be filled out prior to surgery and at 48h post-operatively Other data collected will include a baseline history questionnaire (for demographics, age, sex, weight, income level) and the Public Health Questionnaire (PHQ-9) to measure depression as mood greatly influences pain perception. The PHQ-9 will be used to determine whether groups have been stratified appropriately.

List up to ten relevant references/articles to support the rationale for the research:

1. Bekhit, M.H., Opioid-induced hyperalgesia and tolerance. *Am J Ther*, 2010. 17(5): p. 498- 510. 2. Lin, S.L., et al., Co-administration of ultra-low dose naloxone attenuates morphine tolerance in rats via attenuation of

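### The VAS analysis is left open: the natural reading is up to ten unadjusted t-tests that make no use of the preoperative VAS; one baseline-adjusted comparison per contrast should be pre-specified.

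*Combined protocol and SAP*

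**What the plan says.** The outcome list in Background & Purpose of the Research includes "VAS pain scores measured prior to surgery and at 4, 8 and 12h after extubation", followed by readings at 24 and 48 hours. Statistical Considerations repeats the list: "VAS pain scores measured prior to surgery and at 4, 8 and 12h after extubation and again at 24h and 48h post-operatively". The visit schedule under Study Design uses the same times.

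The analysis rule is one sentence: "For the secondary outcomes, the continuous variables will also be analyzed using 2-sample t-test", applied "to identify the difference between HN and HI group, and between LO and HI group". The form then asks for a breakdown of methods by outcome where needed, and the answer only lists the outcomes again. No key VAS time, per-patient summary, change score, baseline covariate, repeated-measures model or multiplicity rule appears anywhere.

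The only significance level is in the sample-size text, which is "based on a 2-sided 2-sample t-test with a significant level of 0.05". That text plans 35 patients per group and says the investigators "expect to have 96 subjects (account for 8% attrition) for final analysis", which is 32 per group.

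The closure form reports that 8 of the planned 105 were enrolled and that analysis has not yet been done.

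**The concern.** A two-sample t-test needs one value per patient. VAS supplies five postoperative values and the plan does not reduce them to one. Taken as written, the rule therefore leads to a test at each time for each contrast, each at 0.05. Two things follow.

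- With up to ten chances, an isolated p-value below 0.05 on VAS is fairly likely even if neither naloxone nor the remifentanil dose has any effect. Nothing in the plan says how such a result should be read.
- Separate tests do not pool the repeated readings and do not adjust for the preoperative score, although the trial collects both.

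Less postoperative pain is the patient benefit that the rationale puts forward, so a VAS finding would probably be quoted. Because the data are unanalysed, the choice can still be fixed before any comparison is run.

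**Working it through.** **Inputs.** From the documents: 32 analysed per arm (96/3), two-sided 0.05, two contrasts sharing the HI arm, five postoperative VAS times. Assumed, because the documents give no figure: the correlation ρ between postoperative readings (0.3–0.7, with 0.9 as an extreme) and the correlation r between the preoperative and later readings.

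**1. The plan's own figure.** With 32 per arm the noncentral t gives 79.8% power at 0.71 SD and 89.8% at 0.82 SD; the exact detectable effects are 0.7115 and 0.823. The stated 0.71 and 0.82 reproduce. They concern a single t-test; none is given for VAS.

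**2. Number of tests.** 5 times × 2 contrasts = 10.

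**3. Chance of at least one false positive when no arm differs.** If all tests were independent: 1 − 0.95^5 = 22.6% for one contrast and 1 − 0.95^10 = 40.1% for both. These are upper references, since readings are correlated and HI is shared. Simulation of 20,000 three-arm trials per row, equal correlation between readings:

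| ρ | One contrast (5 tests) | Both contrasts (10 tests) |
|---|---|---|
| 0.3 | 21.4% | 35.3% |
| 0.5 | 18.5% | 31.5% |
| 0.7 | 15.0% | 25.6% |
| 0.9 | 10.7% | 18.6% |

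Repeat runs differ by up to about one percentage point, hence the rounded ranges 15–21% and 25–36%. If correlation instead decays with the number of readings between two times (AR(1)), the ten-test figure is 36.2% at 0.3 and 29.5% at 0.7.

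**4. One comparison per contrast.** Testing the per-patient mean of the five readings gives about 5% per contrast and about 9% over both (simulated 8.9–9.1%). The second contrast therefore still needs a rule.

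**5. Precision at the planned size, 80% power.** In units of the single-reading SD, the variance of a mean of five is (1 + 4ρ)/5. Baseline adjustment subtracts r². The detectable effect is 0.7115 × √variance.

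| ρ | Mean of five, unadjusted | r = 0.1 | r = 0.3 | r = ρ |
|---|---|---|---|---|
| 0.3 | √0.44 → 0.47 | √0.43 → 0.47 | √0.35 → 0.42 | 0.42 |
| 0.5 | √0.60 → 0.55 | √0.59 → 0.55 | √0.51 → 0.51 | √0.35 → 0.42 |
| 0.7 | √0.76 → 0.62 | √0.75 → 0.62 | √0.67 → 0.58 | √0.27 → 0.37 |

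So averaging gives 0.47–0.62 SD against 0.71 SD at one time. Adding baseline gives 0.42–0.62 SD if r is 0.1–0.3, and 0.37–0.42 SD only if r equals ρ.

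**6. Early-only effect.** If the effect exists only at 4, 8 and 12 hours, the mean of five carries 3/5 = 0.6 of it. The early effect needed is 0.47/0.6 = 0.79 to 0.62/0.6 = 1.03 SD without baseline adjustment, worse than 0.71 SD at one time. With r = ρ it is 0.37/0.6 = 0.62 to 0.42/0.6 = 0.70 SD, little or no gain.

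**7. Eight patients.** Assuming a 3/3/2 split, ten t-tests give 29–36% for ρ from 0.7 to 0.3. The false-positive problem does not shrink with the sample; the precision figures in steps 5 and 6 no longer describe the data.

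**The case against.** The strongest reply is that the plan never says VAS will be tested separately at five times. A t-test on change from baseline, or on a per-patient mean, would fit the same sentence. That stands. A reader might infer that the plan prescribes ten tests and discards the baseline score; the text does not establish either. What it does establish is that the analysis is unspecified. Separate tests remain the likeliest reading, because the t-test is the only method named, no summary value is defined, and the primary outcome is itself tested at both 24 and 48 hours. Any other intention needs the same added wording.

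A second reply is that VAS carries no hypothesis and no alpha. All stated hypotheses, primary and secondary, concern mechanical pain threshold. This also stands: a reader should not infer that the primary error rate is affected. Calling VAS exploratory, or naming one key time, would limit the multiplicity too, but would not bring the gain from pooling the readings.

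Third, the precision gain is easily overstated. The 0.37–0.42 SD range needs the preoperative score to predict later scores as well as those predict each other. Surgery and postoperative medication come between, and the documents give no correlation. At ρ = 0.9 the unadjusted mean of five detects 0.68 SD, hardly better than 0.71. An average is also weaker than one early reading for a purely early effect.

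A reader might add that each test would use a different set of patients because of missing readings. The documents give only 8% overall attrition, so no size can be put on that.

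**Conclusion.** The concern holds as a gap in specification with a likely consequence. As the text stands, VAS may be tested up to ten times without adjustment and without the preoperative score. Under equal correlation of 0.3–0.7 and 32 per arm, that carries a false-positive chance of about 15–21% per contrast and 25–36% over both; inflation above 5% appeared at every correlation tried. It concerns secondary claims only.

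A single averaged comparison is the better default. The gain is well supported for averaging when the effect is similar across times (0.71 down to 0.47–0.62 SD). The further gain from baseline adjustment is uncertain, because it depends on a correlation that the documents do not give. With 8 patients enrolled, the practical consequence is now about how VAS is reported, not about power.

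**What to change.** Add to the analysis plan:

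- **One VAS comparison per contrast, baseline-adjusted:** ANCOVA on the per-patient mean of the 4, 8, 12, 24 and 48 hour readings with preoperative VAS as covariate, or the average arm difference from a mixed model with baseline VAS. State the weights: three of the five readings fall in the first 12 hours, so an equal-weight mean is not a time average over 4–48 hours.
- **An order for the two contrasts:** HN–HI as the main VAS contrast, with LO–HI tested after it or labelled supportive. Otherwise about 9% remains over the two.
- **Time-specific differences with 95% confidence intervals, labelled descriptive.**
- **For the 8 patients actually enrolled:** report per-patient mean and time-specific VAS descriptively, without significance tests. A full mixed model may not be estimable.

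The cost is a few lines of wording and slightly more analysis work. The real downside is lower sensitivity to an effect confined to the first 12 hours. If that is the effect of interest, the plan should say so and name an early time or an early mean before the data are analysed. Keeping all ten tests with a Bonferroni correction (0.05/10 = 0.005 each) would control the error, but would raise the detectable effect at the planned size to about 0.94 SD.

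### The primary 48h HN–HI t-test can use only patients tested at 48h and ignores their pre-op and 24h thresholds, so loss related to threshold would bias it in a direction the documents do not settle

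*Combined protocol and SAP*

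**What the plan says.** The Background & Purpose section names one primary hypothesis: "The mechanical pain thresholds at 48h in the HN group is higher than in the HI group". The threshold at 24h is tested under a secondary hypothesis.

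Statistical Considerations gives the method: "the 2-sample t-test will be applied to compare the difference in mechanical pain thresholds at 24 and 48h between HN and HI group". The same text appears under Study Design. Each time point has its own test, with no covariate and no repeated-measures model.

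The sample size paragraph uses a "2-sided 2-sample t-test with a significant level of 0.05". It recruits 35 per group, 105 in all, and the investigators "expect to have 96 subjects (account for 8% attrition) for final analysis". This is said to give "80% power to detect an effect size of 0.71 and 90% power to detect an effect size of 0.82".

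Von Frey testing is scheduled before surgery, at 24h and at 48h (Study Design text and visit schedule). The supplied text contains no missing-data method, analysis set, intention-to-treat statement or sensitivity analysis. It does not say why or when the expected 8% are lost.

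The closure form reports 8 of 105 enrolled, data collection complete and analysis still to be done.

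**The concern.** A t-test at 48h has no place for a patient without a 48h value. Leaving such patients out is therefore implied by the method and by the figure of 96, although no rule says so. The plan treats attrition purely as lost sample size, which is enough only if the patients who are lost have the same thresholds, on average, as those who stay.

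The endpoint is a repeated, deliberately painful test after spinal surgery, so a link between threshold and missing the test is plausible. It is an assumption and not something the documents state. If the link exists, the 48h difference among completers is not the difference among all randomised patients. A patient lost after 24h also has two relevant measurements, pre-op and 24h, that the test sets aside. At stake is the size of the primary estimate and, to a smaller degree, its power.

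**Working it through.** **1. The plan's own figures.** From 105 to 96 is a loss of 9/105 = 8.6%. Per arm, 35 × 0.92 = 32.2, rounded to 32, and 3 × 32 = 96. Noncentral-t power, two-sided alpha 0.05, n = 32 per arm: 79.8% at d = 0.71 and 89.8% at d = 0.82. The stated 80% and 90% reproduce, so there is no sample-size error.

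**2. Set-up for the bias check.** From the plan: true HN–HI difference 0.71 SD and loss of about 8.6%. Assumed, because the documents give nothing: the same difference at 24h, SD 1, a 24h–48h correlation of 0.5–0.7, all loss after 24h, and

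logit P(48h missing) = a + b × threshold,

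with a chosen to give the stated loss. Two large-sample estimates are compared:

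- Completers: mean 48h threshold among those tested, HN minus HI. This is what the t-test estimates.
- Using 24h: within each arm, regress 48h on 24h among completers and predict at the mean 24h value of the whole arm. This is what a likelihood model on both time points does.

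**3. Results at about 8.6% loss, true difference 0.71.**

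| How loss arises | Completers | Using 24h |
|---|---|---|
| Unrelated to threshold | 0.71 | 0.71 |
| One rule for both arms, driven by 24h threshold, slope 1–2 per SD, either sign | 0.64–0.69 | 0.71 |
| One rule for both arms, driven by the unseen 48h threshold, slope 1.5, either sign | 0.63–0.64 | 0.65–0.67 |
| Arm-specific, equal rates, same slope 1.5 in each arm | 0.71 | 0.71 |
| Low-threshold HI patients leave, HN loss random (or high-threshold HN leave, HI loss random) | 0.64–0.66 | 0.71 |
| Low-threshold HN patients leave, HI loss random (or high-threshold HI leave, HN loss random) | 0.76–0.78 | 0.71 |
| Low-threshold HI and high-threshold HN leave | 0.56–0.61 | 0.71 |
| High-threshold HI and low-threshold HN leave | 0.82–0.86 | 0.71 |

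A shared rule attenuates whichever end leaves. If high thresholds leave, HN loses more patients and its mean falls more. If low thresholds leave, HI loses more and its mean rises more. Both narrow the gap. Under the shared 24h rule, power of the t-test at this loss is about 74–78%. If loss were 20%, the arm-specific range would widen to 0.39–1.03.

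**4. What the 24h value adds to precision.** If loss is unrelated to threshold and all lost patients have a 24h value, the effective size per arm is

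n_eff = 32 / [1 − ρ²(1 − 32/35)].

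At ρ = 0.5 this is 32.7, and at ρ = 0.7 it is 33.4. Power at 0.71 is then 80.7% and 81.6%, against 79.8%. The gain is small. The reason for the model is protection against bias.

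**5. Actual data.** Eight patients in three arms is 2–3 per arm, if allocation was near equal. Power at d = 0.71 is then 7% (2 per arm) to 10% (3 per arm).

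**The case against.** The strongest reply is that 96 is an ordinary sample-size allowance, not a rule to discard anyone, and that the harm shown at 8–9% loss depends on slopes and correlations the documents do not supply. That is fair, and it keeps the point modest. It does not remove it: the stated method cannot include a patient without a 48h value, and no other method is given.

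A reader might infer that patients in less pain go home early, that the best HN responders are the ones missing, and that the difference is therefore biased toward zero. The documents do not support this. They give no length of stay, discharge rule or reason for loss. Step 3 shows that the bias can be nil or away from zero when loss differs by arm. For the same reason one cannot conclude that the secondary outcome "Opioid consumption required to control pain over the first 24 and 48h post-operatively" is cut short by discharge.

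Nor is a 24h value certain to be in hand. Randomisation follows consent, and surgery is often 3–4 weeks after clearance, so some of the 8% may be lost before surgery or before 24h. The model gains little from those patients.

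Finally, the trial stopped at 8 participants, so 96 of 105 will not be analysed. That stands, and it limits the practical weight for this dataset.

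**Conclusion.** The point holds for the design as written. The primary 48h comparison is a completer t-test that sets aside the pre-op and 24h thresholds, and it is sure to be unbiased only if loss is unrelated to threshold. The direction of any bias cannot be told from the documents. At the plan's own loss it is toward zero under one shared rule driven by the 24h threshold (about 0.64–0.69 for a true 0.71 SD). It ranges over about 0.56–0.86 when the arms may differ. These sizes rest on the assumed slopes, the assumed correlation, and all loss falling after 24h.

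Using the 24h value returns 0.71 whenever loss depends on that value, and also when loss is unrelated to threshold. It is therefore the better method, not just a policy for a gap. It corrects only part of the bias (0.65–0.67) when loss depends on the unseen 48h value. The matter is worth changing but is not a fatal flaw, and the stated power is correct.

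**What to change.** **Design as written.** Replace the separate t-tests for the primary contrast with one likelihood-based repeated-measures model in all randomised patients with at least one post-surgery threshold. The outcomes are the 24h and 48h thresholds. The terms are arm, time and arm by time, with the pre-op threshold as covariate and unstructured covariance. Read the HN–HI contrast at 48h. Report the number, timing and reasons for missing 48h tests by arm. Add a sensitivity analysis for loss that depends on the unseen 48h value, for example imputing the missing values and shifting them by a range of amounts in each arm.

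Do not enter tests done before an early discharge as 48h values. Measurement time would then follow discharge and could differ by arm.

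**Actual data.** With 8 participants an unstructured model may not be estimable. Before analysis, state the analysis set and any exclusions with reasons, and list all 24h and 48h thresholds by arm.

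**Cost.** A wording change, with no extra patients or visits. The model relies on data being missing at random given the observed values, which is weaker than what the completer t-test needs in general, and it recovers little for patients lost before 24h.
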